Efficacy of a Semi-occluded Mask in the Treatment of Patients With Voice Disorder

NCT03410797

February 11, 2020

Basic Study Information

1. * **Title of study:**

Efficacy of a variably-occluded facemask in voice therapy

2. * **Short title:**

Efficacy of a variably-occluded facemask in voice therapy

3. * **Brief description:**

To determine initial efficacy of a semi-occluded facemask on voice outcomes in patients with muscle tension dysphonia (MTD), lesions, and atrophy. We hypothesize that patients will demonstrate an improvement in acoustic, aerodynamic outcomes, and voice handicap index scores following therapy.

4. * **What kind of study is this?**

Single-site study

5. * **Will an external IRB act as the IRB of record for this study?**

Yes No

6. * **Local principal investigator:**

[name]

* **Is this your first submission, as PI, to the Pitt IRB?**

Yes No

7. * **Does the local principal investigator have a financial interest related to this research?**

Yes No

8. **Attach the protocol:**

- Sponsor/Multicenter/Investigator-initiated protocol
- Coordinating Center supplement
- Emergency Use Consent/ Protocol/ FDA Form 3926
- Exempt Application form

Document Category Date Modified Document History

There are no items to display

Funding Sources

1. *** Indicate all sources of support:**

Internal funding

2. *** Provide the source of your Internal funding:**

Study Team Members

1. * Identify each person involved in the design, conduct, or reporting of the research (includes PI):

Name	Roles	Department/School	Affiliation	Involvement in Consent	Qualifications
[name]	Principal Investigator	U of Pgh School of Medicine Otolaryngology	Pitt faculty	yes	[name], PhD is the Co-director of the UPMC Voice Center and Professor, Department of Otolaryngology at the University of Pittsburgh Scho... view all
[name]	Primary Study Coordinator	U of Pgh School of Medicine Otolaryngology Research	Pitt staff	no	

2. External team member information: (Address all study team members in item 1. above and leave this section blank)

Name	Description
There are no items to display	

3. Have you, [name], verified that all members of the research team have the appropriate expertise, credentials, training, and if applicable, child clearances and/or hospital privileges to perform those research procedures that are their responsibility as outlined in the IRB application?

* Yes No

Study Scope

Check all that apply

1. * Will this study actively recruit any of the following populations?

- Adults with impaired decision-making capacity
- Children (under the applicable law of the jurisdiction in which the research will be conducted (<18 years for PA))
- Children who are Wards of the State
- Employees of the University of Pittsburgh/UPMC
- Medical Students of University of Pittsburgh as primary research group
- Students of the University of Pittsburgh
- Neonates of uncertain viability
- Non-viable neonates
- Non-English speakers
- Nursing home patients in the state of Pennsylvania
- Pregnant women
- Prisoners
- N/A

2. * Will any Waivers be requested?

- Waiver/Alteration of Consent
- Waiver to Document Consent
- Waiver/Alteration of HIPAA
- Exception from consent for emergency research
- N/A

3. * Will this study involve any of the following?

- Specimens
- Honest Broker to provide data/specimens
- Return of Results to Subjects or Others
- Fetal tissue
- N/A

4. * Will Protected Health Information be collected?

- Pitt medical records
- UPMC medical records
- Other Institutions' medical records
- N/A

5. * Other Requests?

- Deception (if not Exempt, also requires Waiver/Alteration of Consent)
- Emergency Use / Single Patient Expanded Access (using FDA Form 3926)

- Placebo Arm
- Withdraw from usual care
- N/A

6. *** Determining Scientific Review:**

Department Scientific Review (DOD requires departmental review)

*** Choose the appropriate organization to conduct the scientific review:**

U of Pgh | School of Medicine | Otolaryngology

7. *** Has this study (or substantially similar study) been previously disapproved by the Pitt IRB or, to your knowledge, by any other IRB?**

- Yes No

Review the HRPO policy, if participating in research at the VA Pittsburgh Healthcare System or using funding from the VA

8. *** Does the study use an approved drug or biologic, use an unapproved drug or biologic, or use a food or dietary supplement to prevent, diagnose, cure, treat, or mitigate a disease or condition?**

- Yes No

9. *** Does the study evaluate the safety or effectiveness of a device (includes in-vitro laboratory assays)?**

- Yes No

10. *** Is this application being submitted to convert an approved study from OSIRIS to PittPRO? (Tip Sheet)**

- Yes No

*Download the OSIRIS Transition Continuing Review form, complete and upload below. If you need to attach any additional documents (e.g., data and safety monitoring reports), upload in the Local Supporting Documents page and note the Renewal on the form. **Exempt** submissions in OSIRIS also need to move into PittPRO if they remain ongoing. These will not be considered transitions but new studies. Therefore, Study Scope #10 will be answered as "No." Once the new exempt determination has been issued, the OSIRIS application can be closed. Any exempt submission remaining in OSIRIS by the end of August 2020 will be closed by our office. Please use the "Add Comment" to provide the OSIRIS study number.*

OSIRIS Transition Continuing Review form:

OSIRIS Renewal and Conversion(0.01)

*** OSIRIS ID**

PRO17100675

*** Does your research protocol involve the evaluation or use of procedures that emit ionizing radiation and, after reviewing this HUSC guidance, does your research protocol require HUSC review? (If yes, upload the HUSC form in the Local Supporting Documents section). If you are unsure of review**

requirement, select yes.

Yes No

Research Sites

1. Choose all sites that apply:

UPMC

*** Select the UPMC sites where research will be conducted:**

East

Mercy

Passavant

Other UPMC Site- Specify below:

List the Other UPMC sites:

UPMC Bethel Park

2. Describe the availability of resources and the adequacy of the facilities to conduct this study:

* The UPMC Voice Center has the appropriate space and personnel to study the population indicated in this protocol. The subjects are individuals that are typically seen and evaluated by the clinicians involved in this project.

Devices

1. * List each device in the study that will be evaluated for safety or effectiveness:

Device	Purpose	Type	Attachments
View Semi occluded Mask	This mask is being used as an additional aid in voice therapy. Subjects are being asked to speak into the mask which is thought to enhance voice therapy exercises. The semi-occluded face mask qualifies as a non-significant risk device in that: 1. It is not an implant; 2. It is not used in supporting or sustaining human life; 3. It does not aid in curing, mitigating, or treating disease; 4. It does not present a potential for serious risk to the health, safety, or welfare of the subject.	Exempt from IDE requirements	

2. If applicable, identify each investigational device exemption (IDE) number:

IDE Number	IDE Holder	Other Holder
There are no items to display		

3. Attach files: (attachments may include justification of risk determination, FDA correspondence and if the holder of the IDE is a University of Pittsburgh based, sponsor-investigator, attach both the FDA acknowledgement letter and approval letter)

Document	Category	Date Modified	Document History
There are no items to display			

4. * Describe your plan to manage devices so that they will be used only on subjects and be used only by authorized investigators:

Semi occluded facemasks will only be used by trained speech language pathologists who are participating in this research. The customized grommets that occlude the end of the mask were specifically made for this research study and are not available elsewhere.

Click **Continue** as this page was intentionally left blank.

Recruitment Methods

*** Will you be recruiting individuals for participation in this study?**

Yes No

1. * Describe who will be recruiting individuals for participation for this study:

Study team members also involved in clinical care.

2. * Select all methods to be used for recruitment:

Directly approaching potential subjects (in-person)

3. * Provide details on your recruitment methods:

Individuals will be identified during the course of usual clinical care of patients at the University of Pittsburgh Voice Center. As potential subjects are being clinically evaluated in the University of Pittsburgh Voice Center, they will encounter at least one member of the research team who will be able to determine eligibility through the clinical review of medical records associated with their visit. Once verification of eligibility is obtained, potential subjects will be approached by a member of the research team to review the informed consent document. Any and all questions will be addressed during this time.

4. * Describe all compensation/incentives offered to participants and timing of these offers:

Participants will be paid \$100 in total for completion of the 4 voice therapy sessions and follow-up session. The \$100 payment will be made after the completion of the 5 visits (4 therapy and 1 follow up). There will be no partial payment. Payment will be managed with a reloadable debit card.

Participants will be paid when they present for the follow-up visit after completing 4 voice therapy sessions.

5. Recruitment materials: (attach all material to be seen or heard by subjects, including advertisements and scripts)

Document Category Date Modified Document History

There are no items to display

Study Aims

1. * Describe the purpose, specific aims, or objectives and state the hypotheses to be tested:

To determine the efficacy of a semi-occluded mask in the treatment of patients with voice disorders

To determine initial efficacy of a semi-occluded facemask on voice outcomes in patients with MTD, lesions, and atrophy. We hypothesize that patients will demonstrate an improvement in acoustic, aerodynamic outcomes, and voice handicap index scores following therapy.

2. * Describe the relevant prior experience and gaps in current knowledge including preliminary data. Provide for the scientific or scholarly background for, rationale for, and significance of the research based on existing literature and how it will add to existing knowledge:

Current Semi Occluded Voice Therapy (SOVT) therapies limit the type of vocalizations that can be produced to single vowels, which does not promote learning of the healthy voice behavior in connected speech or generalization to conversation. However, recent preliminary results using a semi-occluded mask indicate that the use of certain mask port diameters may allow for natural speech production while increasing supraglottal pressure and impedance, and thereby result in elicitation of voice with increased efficiency. In addition, the use of a semi-occluded mask provides the possibility for a better transition from phonating single phonemes in therapy to training the target therapy techniques in connected speech.

A healthy voice is essential for communicative activities of daily living.

Approximately 28 million workers in the U.S. experience daily voice problems, which can impair quality of life and work performance. People of all ages, genders, and social statuses suffer from voice problems.⁴ People with voice problems experience worse emotional, physical, and functional impairments than people without voice problems and those with chronic diseases such as sinusitis, angina, and back pain. Voice problems represent a substantial economic cost due to accumulation of short-term disability payments and lost wages.²⁴

Treatment of voice disorders varies but often involves voice therapy and/or surgical intervention. Voice therapy, a non-invasive behavioral treatment for voice disorders, helps patients develop beneficial voice habits, prevents recurrence of voice disorders, and facilitates long-lasting vocal improvement. Many voice therapy techniques involve a semi-occluded vocal tract (SOVT). SOVT treatment is often characterized by sustained (straw phonation, voiced fricatives, nasals), oral oscillatory (lip buzzes, tongue trills, raspberries) or transitory phonation (plosives and glides). Straw phonation therapy, one of the most utilized SOVT methods, was first proposed in 1904 and involved phonating at different pitches into small glass tubes with varying diameters and lengths providing simultaneous semi-occlusion and extension of the vocal tract. Voice therapy exercises involving voice production with a semi-occluded and sometimes lengthened vocal tract have demonstrated

improved vocal efficiency and loudness, reduced mechanical trauma to the vocal fold mucosa, and improved source-filter interaction.

Our group recently developed a semi-occluded facemask for use in patients with and without voice disorders. Recent preliminary results using this semi-occluded facemask indicated that the use of a certain mask port diameters may elicit voice with increased efficiency. A study of 5 participants without voice disorders revealed that a mask occlusion diameter of 6.4 and 3.2 mm resulted in improved vocal efficiency. A study of the immediate effects of a semi-occluded facemask in 20 patients with voice disorders revealed that occlusions diameters of 9.6, 6.4, and 3.2 mm all resulted in significant improvements in acoustic and aerodynamic voice outcomes.

The current study aims to expand upon these past studies by investigating the efficacy of use of a semi-occluded facemask in the treatment of patients with voice disorders.

Study Design

1. **Total number of subjects to be enrolled at this site (enter -1 for chart reviews, banking, registries):**

30

2. **Describe and explain the study design:**

Prospective, experimental

3. **Describe the primary and secondary study endpoints:**

4. **Provide a description of the following study timelines:**

Duration of an individual subject's active participation:

Approximately 6 weeks

Duration anticipated to enroll all subjects:

12-18 months

Estimated date for the investigator to complete this study (complete primary analyses):

12/31/2019

5. **List the inclusion criteria:**

males and females

age 18-60 years old

diagnosed by a multi-disciplinary team consisting of laryngologist and speech-language pathologist with muscle tension dysphonia (MTD) or vocal fold lesions deemed amenable to voice therapy (i.e. not surgical candidates)

6. **List the exclusion criteria:**

Age 61 or older (excluded due to differences in vocal fold tissue structure changes in this age and older)

Under 18 years of age

Current smoker (greater than 5 cigarettes/week)

7. **Will children or any gender, racial or ethnic subgroups be explicitly excluded from participation?**

Yes No

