	Other Risks	-emotional discomfort/uncomfortable feeling (as stated in consent) -potential for skin irritation due to allergy or mild contact pressure

View	Research Activity	voice therapy session
	Common Risks	No Value Entered
	Infrequent Risks	No Value Entered
	Other Risks	rare risk of worsening voice problem

2. * Describe the steps that will be taken to prevent or to minimize risks:

Confidentiality will be maintained as per the usual methods in the Dept. of Otolaryngology. All electronic subject information will be stored on password protected, restricted access servers. Any paper documentation will be maintained in locked file cabinets within the locked offices of the Department of Otolaryngology.

Though uncommon, it is possible that a patient participant's voice could worsen during a voice therapy session. If this occurs, the voice therapist will give the participant the option of discontinuing voice therapy and can refer the patient back to the treating otolaryngologist for repeat vocal fold examination if so desired.

Wearing of the partially occluded mask could potentially be uncomfortable, emotionally for some individuals. The mask is not "fixed" to the individual's face, and can be removed by the subject at any time. The subject is in control of holding the mask over their nose and mouth. In the event of skin allergy/irritation, mask use may need to be discontinued.

3. Financial risks - will the subject or insurer be charged for any research required procedures?

Yes No

4. Describe the steps that will be taken to protect subjects' privacy:

All study related procedures will be performed in private rooms as is typical of the usual clinical care associated with the diagnosis and treatment of the qualifying voice disorders. Information being collected will be limited to the minimum necessary to achieve the specific aims in this study and to lay the groundwork for future research in this area.

5. What steps will be taken in the event that a clinically significant, unexpected disease or condition is identified during the conduct of the study:

All participants will be under the clinical care of physicians in the Department of Otolaryngology. Usual clinical practice procedures will be maintained.

6. Describe the potential benefit that individual subjects may experience from taking part in the research or indicate if there is no direct benefit. Do not include benefits to society or others:

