*** Describe the circumstances and any procedures for orderly termination:**

It is possible that individuals may be removed from participation due to a change in their diagnosis or a change in their treatment plan is recommended.

8. Describe procedures that will be followed when subjects withdraw from the research, including partial withdrawal from procedures with continued data collection and data already collected:

Depending on the circumstances, individuals may be removed from participation and directed to alternative methods of treatment if warranted.

Conflict of Interest

1. * **Is this an FDA Covered Clinical Study?**

Yes No

Answer **YES** if it is:

- A study of a drug or device in humans to be submitted in a marketing application or reclassification petition that the applicant or FDA relies on to establish that the product is effective (including studies that show equivalence to an effective product); or
- A study in which a single investigator makes a significant contribution to the demonstration of safety.

Do **NOT** include:

- phase I tolerance studies or pharmacokinetic studies;
- clinical pharmacology studies (unless they are critical to an efficacy determination);
- large open safety studies conducted at multiple sites;
- treatment protocols; or
- parallel track protocols.

2. * **Does this study involve a Non-Significant Risk Device and you anticipate including the results as part of any type of submission to the FDA for approval of this device?**

Yes No

3. * **Is this study funded in part or whole by a PHS Agency?**

Yes No

4. * **Does any investigator involved in this study (select all that apply):**

- A. Have a financial interest (aggregated value of equity and remuneration during the past or next twelve months) in a publicly-traded entity that either sponsors this research or owns the technology being evaluated or developed that exceeds a 5% ownership interest or a current value of \$10,000?
- B. Receive remuneration (during the past or next twelve months) from a non-publicly traded entity that either sponsors this research or owns the technology being evaluated or developed that exceeds \$10,000?
- C. Have equity in a non-publicly traded entity that either sponsors this research or owns the technology being evaluated or developed?

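### The all-or-nothing $100 payment is forfeited by a participant who stops therapy early for voice worsening or is removed by the team, which works against the plan's own option to stop (minor)

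*Combined protocol and SAP*

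**What the plan says.** **Payment (Recruitment Methods, item 4).** The $100 is "in total for completion of the 4 voice therapy sessions and follow-up session". There are five visits, four for therapy and one for follow-up, and "There will be no partial payment". On timing: "Participants will be paid when they present for the follow-up visit after completing 4 voice therapy sessions". No exception is given for stopping because of harm or for removal by the team.

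**Foreseen harms and the response (Risk and Benefits, items 1 and 2).** For therapy sessions the plan lists a "rare risk of worsening voice problem". If that happens, "the voice therapist will give the participant the option of discontinuing voice therapy", and the therapist can refer the patient back to the treating otolaryngologist for another examination. For the mask, the plan lists skin irritation and emotional discomfort: "In the event of skin allergy/irritation, mask use may need to be discontinued", and the participant can take the mask off at any time.

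**Removal and withdrawal (Risk and Benefits, items 7 and 8).** The team may act without the participant's agreement: "individuals may be removed from participation due to a change in their diagnosis", or when a different treatment plan is advised. Neither answer mentions payment, or follow-up after withdrawal.

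**Undue influence (Consent Process, item 2).** The answer covers time to decide and having no traditional therapy sessions in the meantime. It does not mention payment.

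**Analysis (Study Design, item 8).** The one test named is a paired t-test of VHI-10 against baseline.

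**The concern.** The option to stop is offered for a harm that the plan itself names. Using it before session 4 is complete means that the payment condition can no longer be met. A participant whose voice is getting worse therefore has a financial reason to carry on, which is the opposite of what the safeguard is for. A participant removed by the team loses the same sum without having made any choice.

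There is also a consequence for the data. The paired t-test uses only participants with both a baseline and a follow-up VHI-10. Baseline values come from the medical record, so the follow-up visit is where a value can be lost. An early stopper who would still be willing to attend that visit is paid nothing for doing so. The documents describe no method for missing follow-up values.

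**Working it through.** The plan states no figure to reproduce, and no power, alpha or variance enters. The check sets the payment rule beside the stopping and removal rules.

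**Inputs.** Recruitment Methods, item 4: $100 in total, 4 + 1 = 5 visits, no partial payment. Risk and Benefits, items 2 and 7: the situations in which someone stops or is removed. Study Design: 20 participants in item 8 and 30 in item 1; both are used as a range.

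**Step 1. Payment under the current rule.** Payment = $100 if all four therapy sessions and the follow-up are completed, otherwise $0. So 0, 1, 2, 3 or 4 completed visits pay $0, and 5 pay $100.

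**Step 2. Apply the rule to each situation.** The last column is an illustration with equal shares: $100 / 5 = $20 per visit.

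| Situation | Sessions completed | Follow-up attended | Paid now | At $20 per visit |
|---|---|---|---|---|
| Stops therapy for worsening, does not return | 0 to 3 | no | $0 | $0 to $60 |
| Stops therapy for worsening, returns for follow-up | 0 to 3 | yes | $0 | $20 to $80 |
| Removed by the team before follow-up | 0 to 4 | no | $0 | $0 to $80 |
| Worsens, but completes session 4 and attends follow-up | 4 | yes | $100 | $100 |
| Stops the mask, attends all five visits | 4 | yes | $100 | $100 |

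The first three rows are the established loss. The second row matters most for the analysis: this person would supply the follow-up VHI-10 and is paid nothing, because payment at follow-up requires four completed sessions. The last two rows show where the rule does no harm as written.

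**Step 3. Look for text that softens the rule.** None was found in the compensation answer, the undue-influence answer, the removal and withdrawal answers, or the risk section. The consent form is listed but is not part of the supplied text, so its payment wording could not be checked.

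**Step 4. Cost of paying per visit.**
- Most that a participant with four or fewer visits could receive: 4 x $20 = $80.
- Total outlay cannot exceed what full completion already costs: 20 x $100 = $2,000, or 30 x $100 = $3,000.
- The plan gives no early-stopping rate. Assuming that 10% to 30% stop early for any reason, the number is 0.10 x 20 = 2 to 0.30 x 30 = 9. The added payments are then at most 2 x $80 = $160 to 9 x $80 = $720. This bounds the cost of the fix. It does not estimate how many people are harmed.

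**The case against.** The strongest case on the other side is that the sum is modest, spread over about six weeks; worsening is described as rare; participation is stated to be voluntary, with care not dependent on it; and a completion payment helps retention, which the paired analysis also needs. All of that stands, and it is why the point is minor. None of it alters the forfeiture.

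A reader might also infer several stronger things that the documents do not support:

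- *That anyone who stops for a foreseen harm loses the payment.* For skin irritation the plan foresees stopping the mask, not the visits, and for discomfort it says that the mask can be removed. Payment is tied to visits. The loss would follow only if stopping the mask ended participation, and the plan does not say whether it does.
- *That using the option to stop costs $100 even after four visits.* Once session 4 is complete, no therapy remains to discontinue. A participant harmed at that point who attends follow-up is paid in full. Loss after four completed visits requires missing the follow-up or being removed.
- *That stopping is the plan's only response to worsening.* Referral back to the otolaryngologist is a second one, and all participants remain under physician care.
- *That the rule suppresses reporting and biases a harm rate.* Payment does not depend on what is reported, and a participant can report worsening and continue. The worsening described occurs during a session with the therapist present. An indirect route exists, from report to referral to a changed treatment plan to removal. The follow-up data list has no adverse-event item, and the quarterly meeting topics do not name these harms. So the rule may discourage reporting, but the documents do not show that it does, and they define no harm-rate outcome to be biased.
- *That the before-after estimate is biased in a known direction.* If those who worsened were the ones missing, the mean change would look better than it should. The same payment might also keep poor responders in the study. The direction is not established.

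**Conclusion.** The point holds in a narrow form. A participant who discontinues therapy for voice worsening before completing session 4, or who is removed before completing the visits, forfeits 100% of the $100. The payment rule therefore pulls against the plan's own option to stop. It also leaves early stoppers unpaid for the one visit that yields the follow-up VHI-10.

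This rests on the protocol text alone and on no assumed rate. It does assume that the consent form, which could not be checked, contains no exception. How many participants would be affected is unknown: worsening is called rare, no rate is given for it, and the 10% to 30% early stopping used above is an assumption that serves only to cost the change.

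Severity: minor. It is an avoidable misalignment that is cheap to correct, and it does not invalidate the study.

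**What to change.** 1. **Preferred.** Replace the no-partial-payment rule with payment per attended visit, for example $20 for each of the five visits, maximum unchanged at $100. The reloadable card already planned can carry staged payments.
2. **Minimum alternative.** Keep the completion payment, but pay for visits already attended when a participant stops because of harm or is removed by the team.
3. **In either case,** pay the follow-up share to anyone who attends that visit, including those who stopped therapy early.
4. **Clarify** whether stopping the mask ends participation, and whether a session that is cut short counts as attended. The figures above count completed visits.
5. **Make the consent form agree** with whichever rule is adopted.

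The cost is a wording change to the protocol and, if needed, the consent form, plus at most $80 per participant with four or fewer visits. The incentive to complete becomes slightly weaker, although under item 1 each share, including the one for follow-up, is still paid only on attendance. No therapy, endpoint or clinical rule changes.
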